The principle that asserts that the effect of a treatment policy can be best assessed by evaluating on the basis of the intention to treat a patient (that is, the planned treatment regimen) rather than the actual treatment given. It has the consequence that patients allocated to a treatment group should be followed up, assessed, and analyzed as members of that group irrespective of their compliance to the planned course of

treatment.

IWRS interactive web-response system

legal representative An individual, judicial, or other body authorized under applicable law to consent on

behalf of a prospective patient to the patient's participation in the clinical study.

Lilly Safety System Global safety database that tracks and reports serious adverse and spontaneous events

occurring while using a drug/drug delivery system.

Lower Level Term

metastatic breast cancer

Medical Dictionary for Regulatory Activities

MRI magnetic resonance imaging

NCI National Cancer Institute

NSAI nonsteroidal aromatase inhibitor

ORR objective response rate

OS overall survival

patient A study participant who has the disease or condition for which the investigational

product is targeted.

PD progressive disease

PET positron emission tomography

PFS progression-free survival

PgR progesterone receptor

PK pharmacokinetic

PR partial response

PS performance status

PT Preferred Term

QTc corrected QT interval

randomize the process of assigning patients to an experimental group on a random basis

RANK-L receptor activator of nuclear factor kappa-B ligand

Rb retinoblastoma

RECIST Response Evaluation Criteria in Solid Tumors

reporting database A point-in-time copy of the collection database. The final reporting database is used to

produce the analyses and output reports for interim or final analyses of data.

re-screen to screen a patient who was previously declared a screen failure for the same study

SAE serious adverse event

SAP Statistical Analysis Plan

screen The act of determining if an individual meets minimum requirements to become part of

a pool of potential candidates for participation in a clinical study. In this study, screening involves invasive or diagnostic procedures and/or tests (for example, diagnostic psychological tests, X-rays, blood draws). For this type of screening, informed consent for these screening procedures and/or tests shall be obtained; this

consent may be separate from obtaining consent for the study.

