7.3. Discontinuations

7.3.1. Discontinuation of Patients

The criteria for enrollment must be followed explicitly. If the investigator site identifies a patient who did not meet enrollment criteria and who was inadvertently enrolled, the sponsor must be notified. If the sponsor identifies a patient who did not meet enrollment criteria and who was inadvertently enrolled, the investigator site will be notified. A discussion must occur between the sponsor CRP and the investigator to determine whether the patient may continue in the study, with or without study drug. Inadvertently enrolled patients may be maintained in the study and on study drug when the Lilly CRP agrees with the investigator that it is medically appropriate for that patient. The patient may not continue in the study with or without study drug if the Lilly CRP does not agree with the investigator's determination it is medically appropriate for the patient to continue. The investigator must obtain documented approval from the Lilly CRP to allow the inadvertently enrolled patient to continue in the study with or without studydrug.

In addition, patients will be discontinued from the study treatment (that is, blinded study drug and/or NSAI) and/or from the study in the following circumstances:

• progressive disease (PD) as defined by RECIST v1.1

- enrollment in any other clinical trial involving an investigational drug or enrollment in any other type of medical research judged not to be scientifically or medically compatible with this study
- investigator decision
 - the investigator decides that the patient should be discontinued from the study or study treatment
 - o if the patient, for any reason, requires treatment with another therapeutic agent that has been demonstrated to be effective for treatment of the study indication, discontinuation from the study treatment occurs prior to introduction of the new agent
- patient decision
 - o the patient or the patient's designee (for example, legal guardian) requests to be withdrawn from the study or study treatment
- sponsor decision
 - Lilly stops the study or stops the patient's participation in the study for medical, safety, regulatory, or other reasons consistent with applicable laws, regulations, and good clinical practice (GCP)

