The reason and date of discontinuation will be collected for all patients. All randomized patients who discontinue regardless of whether or not they received study drug, will have procedures performed as shown in the Study Schedule (Attachment 1).

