8.1. Summary of Study Design

Study JPBM is a multicenter, randomized, double-blind, placebo-controlled, Phase 3 study evaluating treatment of LY2835219 with NSAI or placebo with NSAI in postmenopausal women with HR+, HER2- locoregionally recurrent (not amenable to curative therapy) or metastatic breast cancer who have not received prior systemic therapy in this disease setting.

Figure JPBM.8.1 illustrates the study design.

Abbreviations: HER2- = human epidermal growth factor receptor 2-negative; HR+ = hormone receptor-positive; N = number; NSAI = nonsteroidal aromatase inhibitor; PD = progressive disease.

Figure JPBM.8.1. Illustration of study design.

Approximately 450 patients will be randomized 2:1 between the 2 arms:

- Experimental Arm A: LY2835219 150 mg orally every 12 hours on Days 1 to 28 plus either anastrozole 1 mg or letrozole 2.5 mg once daily of a 28-day cycle
- Control (Placebo) Arm B: Placebo orally every 12 hours on Days 1 to 28 plus either anastrozole 1 mg or letrozole 2.5 mg once daily of a 28-day cycle

Patients will be randomized using the following stratification factors: nature of disease (visceral metastases versus bone-only metastases versus other) and prior (neo)adjuvant endocrine therapy (aromatase inhibitor therapy versus other versus no prior endocrine therapy). The presence of visceral metastases refers to lung, liver, pleural, peritoneal, or adrenal gland involvement at the time of randomization. Prior (neo)adjuvant endocrine therapy refers to aromatase inhibitor therapy (e.g., anastrozole, exemestane and letrozole) vs. other (e.g., tamoxifen and fulvestrant) vs. no prior endocrine therapy.

Database lock for the interim analysis for efficacy will occur when approximately 218 investigator-assessed PFS events have been observed. Database lock for the primary analysis of the PFS endpoint will occur when approximately 312 investigator-assessed PFS events have been observed. The final analysis of OS will occur when approximately 315 OS events have been observed. All patients will be followed for survival information until death or study completion, whichever comes first.

[figure not shown]
Terms used to describe the periods during the study are defined below:

- Baseline: begins when the ICF is signed and ends at the first study treatment dose (or at discontinuation, if no treatment is given). This may be up to 28 days prior to the first study treatment dose.

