10.1.2. Efficacy Assessments during Postdiscontinuation Follow-Up

Postdiscontinuation follow-up during the study period will be conducted as described in the Study Schedule (Attachment 1).

For those patients who discontinue study treatment without objectively measured PD, the investigative sites will continue to monitor patients and periodically evaluate tumor response approximately every 8 weeks for the first 18 months following randomization and thereafter approximately every 12 weeks by the same method used at baseline and throughout the study until the patient has objective disease progression, or until the primary analysis of PFS. In addition, anticancer therapies initiated after study treatment discontinuation will be collected during this follow-up period. After the patient has objective disease progression, radiologic imaging and photographic images are no longer required and the patient will be followed up approximately every 12 weeks until the patient's death or overall study completion.

Lilly will continue to collect survival data on all patients but may reduce data collection for other efficacy data. Lilly will notify investigators when this reduced data collection can begin.

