Tumor Assessment continued	X-ray, CT scan with bone windows, or MRI	Section 10.1.1 Attachment 5	X	X	ONLY For patients who discontinue study treatment without objectively measured progressive disease (PD), focused studies are performed for patients with bone lesions previously identified by bone scintigraphy. During long term follow up period, repeat scans should performed approximately every 8 weeks for the first 18 months following randomization, and subsequently approximately every 12 weeks until disease progression or study completion.
Survival Informat	tion	Section 10.1.4	X	X	Although preferable to collect during a clinic visit, survival information may be collected by contacting the patient or family directly (for example, via telephone) if no procedures required. This should be collected at minimum every 90 days if no other procedures are performed. Additional long-term follow-up data collection will include post-discontinuation anticancer therapies.
Adverse Events C Grading	ollection/CTCAE	Section 10.3	X	X	After Visit 801, only study protocol or drug-related events are reported. If a patient has ongoing AE or SAE possibly related to study drug (not coadministered drug) (for instance, abnormal electrolytes), the patient should be followed until the event is resolved, the event is no longer considered to be drug-related, the event becomes stable or returns to baseline, a new treatment is initiated for the patient, or the patient dies or is lost to follow-up. Any subsequent follow-up(s) for AEs will be no more than 30 days \pm 5 days in duration.
Concomitant Med	lications Notation	Section 9.6	X		
	Central hematology	Attachment 2	X		
Lab/ Diagnostic	Central chemistry	Attachment 2	X		
Tests	Biomarker plasma sample	Section 10.4.2	X		Draw sample only for patients discontinuing due to PD.
	ECG	Section 10.3.2.1	X		Patients must be supine for approximately 5 to 10 minutes before ECG collection and remain supine but awake during ECG collection.
Health Outcomes	EORTC QLQ-C30, EORTC QLQ-BR23, EQ-5D 5L	Section 10.2	X		

Protocol I3Y-MC-JPBM Post Treatment Discontinuation Study Schedule

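### Section 7.3.1 can be read as ending all participation of a patient randomized in error when the sponsor physician disagrees, which conflicts with the protocol's follow-up rules for all randomized patients

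*Protocol*

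**What the plan says.** **The rule on inadvertent enrollment (Protocol 7.3.1).** When a randomized patient turns out not to have met the entry criteria, the sponsor physician and the investigator discuss whether she may go on, on or off drug. If they do not agree: "The patient may not continue in the study with or without study drug if the Lilly CRP does not agree". Documented approval from the sponsor physician is needed for her to go on, again on or off drug. The next paragraph treats leaving treatment and leaving the study as different things: patients may be "discontinued from the study treatment (that is, blinded study drug and/or NSAI) and/or from the study in the following circumstances".

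**The rules on follow-up.**
- Protocol 7.3.1, closing paragraph: "All randomized patients who discontinue regardless of whether or not they received study drug, will have procedures performed as shown in the Study Schedule". For patients off treatment, that schedule (Attachment 1) contains tumor assessment until objective progression and survival information. On survival it says: "This should be collected at minimum every 90 days if no other procedures are performed".
- Protocol 8.1: "All patients will be followed for survival information until death or study completion, whichever comes first".
- Protocol 10.1.2: "Lilly will continue to collect survival data on all patients".
- Protocol 12.2.14.2, on interim efficacy analyses, keeps every patient in follow-up for PFS up to the primary PFS analysis and for OS up to study close.
- The glossary entry on intention to treat (Abbreviations and Definitions): "patients allocated to a treatment group should be followed up, assessed, and analyzed as members of that group irrespective of their compliance".

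**The analysis set.** Protocol 12.2.1 and SAP 6.1.1 both put every randomized patient in the intention-to-treat population.

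**The concern.** Section 7.3.1 ties together two decisions that should be separate: whether the patient stays on treatment, and whether her outcomes go on being recorded. For a patient off treatment, being in the study consists of the post-discontinuation follow-up defined in Section 8.1. A rule that bars her from the study even off drug therefore appears to bar that follow-up, while the closing paragraph of the same section tells the site to carry it out.

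At stake is completeness of follow-up for the primary endpoint (PFS) and the alpha-controlled secondary endpoint (OS). The decision is made case by case after randomization, and Section 9.5.3 concedes that treatment-related signs and symptoms can reveal the assignment. Outcomes that are not collected cannot be recovered at analysis. SAP 6.2 imputes nothing except dates, and none of the four numbered PFS sensitivity analyses in SAP 6.7.5.1 addresses removal by the sponsor.

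**Working it through.** **1. The passages side by side.**

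| Place | Who is covered | What happens |
|---|---|---|
| 7.3.1, inadvertent enrollment | Ineligible randomized patient, sponsor physician disagrees | No continuation in the study, on or off drug |
| 7.3.1, closing paragraph | All randomized patients who discontinue | Attachment 1 procedures |
| 8.1 and 10.1.2 | All patients | Survival follow-up and survival data |
| 12.2.14.2 | All patients | PFS and OS follow-up continue |
| 9.5.2, emergency unblinding | Unblinded patient | Treatment stops; long-term follow-up expressly continues |

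The first row has no sentence like that in the last, and the middle rows have no exception for patients enrolled in error.

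**2. What happens in the analysis if a site follows the first row.** The patient stays in the intention-to-treat set. In the PFS censoring tables (Protocol Table JPBM.12.1, SAP Table JPBM.6.1), rule 4 names loss to follow-up and withdrawal of consent, not removal by the sponsor. Rule 2 would censor her at randomization if she has no post-baseline assessment; rule 3 would otherwise censor her at the last adequate assessment. For OS she is censored at the date last known alive (Protocol 10.1.4) or at last contact before the cutoff (SAP 6.7.3.2).

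**3. Size.** First the plan's own figures, by Schoenfeld's formula with 2:1 allocation, so p(1−p) = 2/9.
- Events needed (Protocol 12.1: hazard ratio 0.714, one-sided alpha 0.025, power 80%): (1.960 + 0.842)² / [(2/9) × (ln 0.714)²] = 7.849 / (0.2222 × 0.1135) ≈ 311.2, rounded up to 312. This reproduces the protocol.
- Power with 312 events: Φ(√(312 × 2/9) × 0.3369 − 1.960) = Φ(0.845) = 80.1%. The protocol states at least 80%.
- Power with 240 events (SAP 5.2: hazard ratio 0.67; final boundary 0.0249993 from SAP 6.7.2.2): Φ(√(240 × 2/9) × 0.4005 − 1.960) = Φ(0.965) = 83.3%. The SAP states more than 80%.

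The documents do not say how many patients would be removed. As an assumption, let 0.5% to 5% of 450 be lost (2.25 to 22.5 patients), with events reduced in proportion and never made up.

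| Lost | Events, protocol design | Power | Events, SAP design | Power |
|---|---|---|---|---|
| 0% | 312 | 80.1% | 240 | 83.3% |
| 0.5% | 310.4 | 79.9% | 238.8 | 83.1% |
| 5% | 296.4 | 78.1% | 228.0 | 81.3% |

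The PFS analyses are triggered by event counts, so waiting for the planned number removes this loss. For OS, 315 deaths are 315/450 = 70.0% of all patients. With the same losses they would be 315/(450 × 0.995) = 70.4% to 315/(450 × 0.95) = 73.7% of those still followed. The effect is a somewhat later analysis, plus whatever bias the censoring brings.

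**The case against.** The strongest reply is that Section 7.3.1 answers itself. Its closing paragraph covers every randomized patient who discontinues, without exception, and the sentence on disagreement never mentions scans, survival contacts or follow-up. A site could end her participation and still perform the Attachment 1 procedures. This stands in part. A reader might infer that the protocol orders scans and survival contacts to stop, but the text does not say so; that is an inference which the closing paragraph opposes. The conflict remains, because the bar on going on expressly reaches patients off drug and the section distinguishes treatment from study. Section 9.5.2 shows that the protocol says follow-up continues where it means to.

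A second reply is that intention to treat is not violated. For the analysis set this is right: she is still analyzed as randomized. Only the follow-up half of the glossary principle is touched, and a glossary entry is not an operating rule.

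A third is that bias is unlikely. The stated test is medical appropriateness, and the veto belongs to the sponsor physician. Section 8.2 denies the sponsor study team immediate access to assignments, and Section 10.3.3 has the sponsor review deaths and serious adverse events blinded. The remark in 9.5.3 concerns the investigator, site staff and the patient. This also stands: informative censoring is possible, since the investigator takes part in the discussion, but the documents do not show it to be likely.

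Finally, the rule applies only when a patient is ineligible, the investigator wants her to go on, and the sponsor physician disagrees. No rate is given for any of these, so the number is probably small.

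**Conclusion.** The point holds as an unreconciled conflict over follow-up. Read plainly, the sentence on disagreement in 7.3.1 ends off-drug participation, against the closing paragraph of that section and Sections 8.1, 10.1.2 and 12.2.14.2. If it is followed, patients who remain in the intention-to-treat set lose PFS and OS follow-up through a discretionary decision taken after randomization.

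It does not hold as a claim that the protocol clearly stops follow-up, that the analysis set is breached, or that the trial loses meaningful power. Even at an assumed 5% lost with no events made up, power falls by about 2 percentage points (80.1% to 78.1%, or 83.3% to 81.3%), and event-driven timing largely restores it. What remains is avoidable and possibly informative censoring in probably few patients.

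The conclusion rests on the protocol approved in September 2014. The SAP's revision history refers to protocol amendments (a) and (b), which were not supplied. Later wording of 7.3.1 could not be checked, and the difference between 312 and 240 events is not treated as an error.

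**What to change.** Check first whether a later amendment already settles this. If not, reconcile 7.3.1 with its own closing paragraph and with Sections 8.1, 10.1.2 and 12.2.14.2 by adding a sentence to this effect: whatever is decided about treatment, tumor assessment and survival data collection per Attachment 1 continue for every randomized patient unless she withdraws consent. Limit the wording on staying in the study, and on documented approval, so that neither ends data collection.

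The treatment decision stays where 7.3.1 puts it, and no clinical rule is proposed. The cost is a clarifying sentence and matching edits in a protocol amendment. It adds no patients and no procedures beyond those already in Attachment 1.

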7.3.2. Discontinuation of Study Sites

Study site participation may be discontinued if Lilly, the investigator, or the ethical review board (ERB) of the study site judges it necessary for medical, safety, regulatory, ethical, or other reasons consistent with applicable laws, regulations, and GCP.

7.3.3. Discontinuation of the Study

[figure not shown]
The study will be discontinued if Lilly judges it necessary for medical, safety, regulatory, ethical, or other reasons consistent with applicable laws, regulations, and GCP.

8. Investigational Plan

8.1. Summary of Study Design

Study JPBM is a multicenter, randomized, double-blind, placebo-controlled, Phase 3 study evaluating treatment of LY2835219 with NSAI or placebo with NSAI in postmenopausal women with HR+, HER2- locoregionally recurrent (not amenable to curative therapy) or metastatic breast cancer who have not received prior systemic therapy in this disease setting.

Figure JPBM.8.1 illustrates the study design.

Abbreviations: HER2- = human epidermal growth factor receptor 2-negative; HR+ = hormone receptor-positive; N = number; NSAI = nonsteroidal aromatase inhibitor; PD = progressive disease.

Figure JPBM.8.1. Illustration of study design.

Approximately 450 patients will be randomized 2:1 between the 2 arms:

- Experimental Arm A: LY2835219 150 mg orally every 12 hours on Days 1 to 28 plus either anastrozole 1 mg or letrozole 2.5 mg once daily of a 28-day cycle
- Control (Placebo) Arm B: Placebo orally every 12 hours on Days 1 to 28 plus either anastrozole 1 mg or letrozole 2.5 mg once daily of a 28-day cycle

Patients will be randomized using the following stratification factors: nature of disease (visceral metastases versus bone-only metastases versus other) and prior (neo)adjuvant endocrine therapy (aromatase inhibitor therapy versus other versus no prior endocrine therapy). The presence of visceral metastases refers to lung, liver, pleural, peritoneal, or adrenal gland involvement at the time of randomization. Prior (neo)adjuvant endocrine therapy refers to aromatase inhibitor therapy (e.g., anastrozole, exemestane and letrozole) vs. other (e.g., tamoxifen and fulvestrant) vs. no prior endocrine therapy.

Database lock for the interim analysis for efficacy will occur when approximately 218 investigator-assessed PFS events have been observed. Database lock for the primary analysis of the PFS endpoint will occur when approximately 312 investigator-assessed PFS events have been observed. The final analysis of OS will occur when approximately 315 OS events have been observed. All patients will be followed for survival information until death or study completion, whichever comes first.

[figure not shown]
Terms used to describe the periods during the study are defined below:

- Baseline: begins when the ICF is signed and ends at the first study treatment dose (or at discontinuation, if no treatment is given). This may be up to 28 days prior to the first study treatment dose.
- **Study Period:** begins at the first study treatment dose and ends at study completion. The study period does not include the continued access period.
 - o **Study Treatment Period:** begins at the first study treatment dose and ends when the patient and the investigator agree that the patient will no longer continue study treatment. This date is to be reported on the electronic case report form (eCRF) as the Date of Discontinuation from study treatment.
- **Postdiscontinuation Follow-Up:** begins the day after the patient and the investigator agree that the patient will no longer continue study treatment.
 - Short-term follow-up begins the day after the patient and the investigator agree that the patient will no longer continue study treatment and lasts approximately 30 days.
 - o *Long-term follow-up* begins the day after short-term follow-up is completed and continues until the patient's death or overall study completion.
- Continued Access Period: begins after study completion and ends at the end of trial. During the continued access period, patients on study treatment who continue to experience clinical benefit may continue to receive study treatment (except placebo) until one of the criteria for discontinuation is met.
 - The continued access period includes continued access period short-term followup.
 - O Continued access short-term follow-up: begins the day after the patient and the investigator agree that the patient will no longer continue treatment in the continued access period and lasts approximately 30 days.

